2.3. Study Design

Overview of Study Design and Key Features	

The diagram illustrates the study design timeline. It is divided into three main phases: Screening Phase, Maintenance Phase, and Extension Phase. The Screening Phase (Day 1) involves randomization (1:1, N=570) into two arms: 'PI, NNRTI or INI Based Regimen with 2 NRTI Backbone' and 'Oral CAB + RPV'. The Maintenance Phase (Day 1 to Week 52) continues with 'PI, NNRTI or INI Current ART' for the first arm and 'CAB LA + RPV LA' for the second. At Week 52, the first arm has an optional 'Extension Phase' (Oral CAB + RPV), while the second arm enters an 'Extension Phase'. Both arms have a '1° Endpoint' at Week 48 and a '2° Endpoint' at Week 96. 'Q4 Weeks' intervals are marked between Week 48 and Week 52, and between Week 56 and Week 96.
	

N=570, randomized 1:1 to each arm and stratified by baseline 3rd Agent class and sex at birth. # Must be on uninterrupted current regimen (either the initial or second cART regimen) for at least 6 months prior to Screening. Documented evidence of at least two plasma HIV-1 RNA measurements <50 c/mL in the 12 months prior to Screening: one within the 6 to 12 month window, and one within 6 months prior to Screening. No history of virologic failure. No evidence of viral resistance based on the presence of any resistance-associated major INI, or NNRTI mutation (except K103N) from prior genotype assay results. No current or prior history of etravirine use. ΨINI based regimen excludes abacavir/dolutegravir/lamivudine (TRIUMEQ), and INI therapy will be capped at approximately 40% of study enrolment for current ART †Optional Extension Phase to CAB LA + RPV LA at Wk 52 for participants randomized to current ART ‡Participants who withdraw from IM arm must go into 52 week long term follow up phase
	
Design Features	
 Phase III, randomized, open-label, active-controlled, multicenter, parallel-group, non-inferiority study designed to assess the antiviral activity and safety of a two-drug regimen of CAB LA + RPV LA compared with maintenance of current ART The ATLAS study comprises a Screening Phase (up to 35 days), a Maintenance Phase (Day 1 to Week 52), and the randomized portion of the study will continue with an Extension Phase up to at least 96 weeks. Additionally, any participant who receives at least a single dose of CAB LA and/or RPV LA and discontinues the CAB LA + RPV LA regimen will enter the Long-term Follow-up Phase and will initiate highly active antiretroviral therapy (HAART) for at least 52 weeks after the last dose of CAB LA and/or RPV LA
Dosing	
 Maintenance Phase: 1:1 randomization to continue current ART or be switched to the CAB LA + RPV LA regimen through 52 weeks Extension Phase: CAB LA + RPV LA
Treatment Assignment	
 N =570 randomized at start of Maintenance Phase At Week 52, participants randomized to continue on current ART will have the option to either continue study participation by switching to CAB LA + RPV LA in the Extension Phase, or to complete their study participation at

Overview of Study Design and Key Features	
	Week 52. 
 • GSK RandAll NG used to generate randomization schedules • Stratified Randomization by baseline third agent class (PI, INI, or NNRTI) and sex at birth.
Interim Analysis	
 • 50% of subjects completing Week 24 • Continuous time monitoring of confirmed virologic failure (CVF) (both in the NNRTI strata and overall) • The main analysis will be conducted to evaluate the primary objective of the protocol at Week 48. • Further data cuts and analyses may be conducted as necessary in order to support regulatory submissions and publications.

2.4. Statistical Hypotheses / Statistical Analyses

The study is designed to demonstrate that the antiviral effect of switching to CAB LA + RPV LA (CAB) is non-inferior to continuation of current first line antiretroviral regimen (current ART) at Week 48 in HIV-1 infected ART-experienced participants. Non-inferiority in the proportion of participants with HIV-1 RNA ≥ 50 copies/mL at Week 48 (per FDA's snapshot algorithm) can be concluded if the upper bound of a two-sided 95% confidence interval for the difference in the proportion of subjects with HIV-1 RNA ≥ 50 copies/mL between the two treatment arms (CAB – current ART) is less than 6%.

If f_{ia} is the rate of subjects with HIV-1 RNA ≥ 50 c/mL on CAB LA + RPV LA and f_c is the rate of subjects with HIV-1 RNA ≥ 50 c/mL (per FDA snapshot algorithm) for the Current ART arm then the hypotheses can be written as follows:

$$H_0: f_{ia} - f_c \geq 6\% \quad H_1: f_{ia} - f_c < 6\%$$

In the pooled analysis of the two studies, as described in the clinical summary analysis plan, a 4% non-inferiority margin will be used.

3. PLANNED ANALYSES

At least two analyses will be conducted to evaluate primary and secondary objectives of the protocol, one after all subjects have completed their visit at Week 48 and one after Week 96. Further data cuts and analyses may be conducted as necessary after Week 96 in order to support regulatory submissions and publications. The Week 48 analysis will be primary, at which primary and secondary comparisons between arms will be performed. There will be no comparison between treatment arms at Week 96 analyses. An IDMC analysis will be conducted when about 50% subjects have completed Week 24, and a final End-of-Study (EOS) analysis will be conducted when all subjects have completed the study.

3.1. Interim Analyses

An Independent Data Monitoring Committee (IDMC) will be instituted to ensure external objective medical and/or statistical review of efficacy and safety in order to protect the ethical interests and well-being of subjects and to protect the scientific validity of this study and study 201584.

An IDMC will evaluate accumulating efficacy, tolerability / safety, and PK of CAB LA + RPV LA at predetermined times during the study. An interim futility analysis will be performed with the intent of having approximately 50% of participants reaching Week 24 and providing sufficient lead time to allow the IDMC to review the data prior to any participants reaching the Week 48 visit. A futility rule based on Bayesian posterior predictive probability approach will be applied to assess the probability that CAB LA + RPV LA injectable regimen would demonstrate non-inferiority to the continued the Current ART arm given the partial data set. The Sponsor will remain blinded to this analysis.

In addition, the IDMC may also monitor the incidence of participants meeting confirmed virologic failure criteria until all subjects complete Week 24 to ensure that participants are not being sub-optimally treated in the CAB + RPV LA arm.

Full details of the analyses, estimated timing and the decision criteria that will be used to determine regimen performance will be pre-specified in the IDMC Charter.

3.2. Final Analyses

The primary analysis will be conducted to evaluate the primary objective of the protocol at Week 48. These analyses will be performed after the completion of the following sequential steps:

1. All subjects have completed Week 48 and had a re-test if necessary.
2. All required database cleaning activities have been completed and final database release and database freeze has been declared by Data Management.
3. All criteria for unblinding the randomisation codes have been met.
4. Randomization codes have been distributed according to Ramos NG procedures.

4. ANALYSIS POPULATIONS

Population	Definition / Criteria	Analyses Evaluated
All Subjects Screened Population	
 Comprised of all subjects screened for inclusion in the study. Subjects may be re-screened once, for which they will receive a new subject number. Only the latest re-screening data will be included in the screening population summaries/analyses but all screening data will be listed. 	
 Study Population
All Participants Randomized Population	
 All randomized participants 	
 Secondary population for some analyses
Intent-to-Treat Exposed Population (ITT-E)	
 All randomized participants who receive at least one dose of IP during the Maintenance Phase of the study (on or after Day 1 visit). Participants will be analysed according to the randomized treatment regardless of what treatment was actually received. 	
 Study Population Efficacy
Per-Protocol (PP)	
 Consist of all participants in the ITT-E Population with the exception of those with important protocol deviations leading to exclusion from PP population. Important protocol deviations that would exclude subjects from the PP population are defined in Section 4.1 (Protocol Deviations) and Appendix 1 (Protocol Deviation Management and Definition for Per-Protocol Population). 	
 Efficacy (Sensitivity Analysis)
Safety population	
 All randomized participants who receive at least one dose of IP during the Maintenance Phase of the study (on or after Day 1 visit). Participants will be assessed according to actual treatment received 	
 Safety
Extension Switch Population (ESP)	
 All randomized subjects from Current ART arm who receive at least one dose of CAB and/or RPV during the Extension Phase of the study. 	
 Safety and efficacy
The Safety Long-Term Follow-up Population (LTFU)	
 All subjects receiving at least one dose of CAB LA and/or RPV LA who have discontinued the CAB LA+ RPV LA regimen and have a least one Long-Term Follow-up phase clinic visit. 	
 Safety
PK Population	
 All participants who receive CAB and / or RPV and undergo PK sampling during the study, and provide CAB and /or RPV plasma concentration data. 	
 PK
Confirmed Virologic Failure	Comprised of all subjects in the ITT-E population who met Confirmed Virologic Failure (CVF)	
 Genotypic Phenotypic

Population	Definition / Criteria	Analyses Evaluated
(CVF) Population	criteria. *CVF is defined as: Rebound as indicated by two consecutive plasma HIV-1 RNA levels ≥ 200 c/mL after prior suppression to < 200 c/mL	
 IDMC CVF Analysis
Futility Analysis Population at Week 24	
 Comprised of all subjects in the ITT-E population and who started study treatment at least 169 days prior to the IDMC cut-off date (in order to account for subjects who withdrew early but would have achieved Week 24) 	
 IDMC Futility Analysis

NOTES:

- Please refer to [Appendix 13](#): List of Data Displays which details the population to be used for each display being generated.

4.1. Protocol Deviations

- Important protocol deviations (including deviations related to study inclusion/exclusion criteria, conduct of the trial, patient management or patient assessment) will be summarised and listed.
- Important deviations which result in exclusion from the analysis population will also be summarised and listed. (Please refer to [Appendix 1](#): Protocol Deviation Management and Definitions for Per Protocol Population)].
- Protocol deviations will be tracked by the study team throughout the conduct of the study in accordance with the Protocol Deviation Management Plan.
 - Data will be reviewed prior to freezing the database to ensure all important deviations and deviations which may lead to exclusion from the analysis are captured and categorised on the protocol deviations dataset.
 - This dataset will be the basis for the summaries and listings of protocol deviations.
- A separate summary and listing of all inclusion/exclusion criteria deviations will also be provided. This summary will be based on data as recorded on the inclusion/exclusion page of the eCRF.

5. CONSIDERATIONS FOR DATA ANALYSES AND DATA HANDLING CONVENTIONS

5.1. Study Treatment & Sub-group Display Descriptors

Treatment Group Descriptions			
RandAll NG Randomization System		Data Displays for Reporting	
Code	Description	Description	Order in TLF
A	CAB LA + RPV LA	Q4W IM	1
B	Current ART	Current ART	2

Treatment comparisons will be displayed as follows using the descriptors as specified:

Q4W IM vs Current ART

5.2. Baseline Definitions at Maintenance

Baseline is referred to Baseline at Maintenance, unless otherwise specified. For all endpoints (except as noted in baseline definitions) the baseline value will be the latest pre-treatment (see [Table 9](#)) assessment with a non-missing value, including those from unscheduled visits. If time is not collected, Day 1 assessments are assumed to be taken prior to first dose and used as baseline.

Electrocardiograms (ECGs) are to be performed in triplicate on Day 1 visit. The baseline value for an ECG parameter will be the mean of the last pre-treatment set of assessments from the same date, so long as at least one of the triplicate assessments is available.

Unless otherwise stated, if baseline data is missing no derivation will be performed and baseline will be set to missing.

5.3. Multicentre Studies

Data will be summarized for all centres combined. Country will be treated as an exploratory subgroup for analyses of the primary efficacy endpoint as described in Section [7.1.5.1](#). Some countries will be combined for exploratory subgroup analyses with consideration due to the number of participants enrolled. These include (but are not limited to) those identified below

Region	Countries
Latin America	Argentina + Mexico

5.4. Examination of Covariates, Other Strata and Subgroups

5.4.1. Covariates and Other Strata

The list of covariates and other strata may be used in descriptive summaries and statistical analyses, some of which may also be used for subgroup analyses. Additional covariates and other strata of clinical interest may also be considered.

Category	Details
Strata	
Randomization Strata:
 
For the proportion of participants with plasma HIV-RNA greater than or equal to 50 copies/mL per FDA Snapshot algorithm at Week 48 (primary endpoint), a stratified analysis with Cochran-Mantel Haenszel weights will be used to adjust the primary treatment comparison for the randomization strata corresponding to sex at birth and third agent class at entry). A similar approach will be used to adjust the analysis of the proportion of participants with HIV-1 RNA <50 c/mL (per the FDA's Snapshot algorithm) at Week 48 (key secondary endpoint).
 
See Section 7.1.5.1 for additional details on the statistical analysis methodology.

Other Subgroups/Covariates	See details in Section 5.4.2

5.4.2. Examination of Subgroups/Covariates

The following is a list of subgroups that may be used in descriptive summaries and statistical analyses. Additional subgroups of clinical interest may also be considered.

- If the percentage of subjects is small within a particular subgroup, then the subgroup categories may be redefined prior to unblinding the trial.
- If the category cannot be refined further, then descriptive rather than statistical comparisons may be performed for the particular subgroup.
- For subgroup analysis, per European Medicines Agency Guideline on the investigation of subgroups in confirmatory clinical trials (EMA, 2013), factors defining a subgroup population may be put in three categories:
 EMA Subgroup Category 1: Factors with strong reason to expect a heterogeneous response to treatment. In this case separate trials should usually be planned. There are no factors falling into this category in this study.

EMA Subgroup Category 2: Factors with at least some biological plausibility or external evidence such that a heterogeneous response might be hypothesized. In this study, stratified randomisation strata, key demographic factors, Baseline CD4, CDC stage will be fall into this category. For these factors, subgroup analyses will be performed but likely underpowered so that a formal proof of efficacy will not be available individually in all subgroups. If consistent findings across multiple

comparisons were observed then these analyses would still be suggestive of a generalizable finding from the overall population.

EMA Subgroup Guideline Category 3: Factor with good argumentation why homogeneity of response to treatment is plausible. The impact of factors falling into this category will be explored.

- Additional covariates of clinical interest may also be considered.

Category	Covariates and / or Subgroups
EMA Subgroup Category 2:	
Stratified Randomisation Strata	
 • Baseline third agent class (PI, INI, NNRTI) • Sex at birth (Male, Female) 
For analysis purposes, randomization strata will be derived using eCRF data, even if this differs from the strata captured in RAMOS NG.
 
All statistical analyses will adjust for the above randomization strata, unless stated otherwise. Treatment-by-Strata interactions will be assessed as specified in the analysis sections.

Demographic and Baseline Characteristic Subgroups	
 • Age: 
 ○ <35; 35-<50; ≥50 (for statistical modelling on efficacy analysis of PK/PD and health outcome, the first two groups will be consolidated, i.e. <50, ≥50) 
For the Table of summary of demographic characteristics only, the following age group should also be presented: ≤18, 19-64, ≥65 (FDAAA requirement) 18-64, 65-84, ≥85 (EMA requirement)
 • Race: 
 ○ White; Non-White ○ Black/ African American; Non- Black/ African American • Country 
 ○ Argentina ○ Mexico ○ Australia ○ Canada ○ France ○ Germany ○ Italy

Category	Covariates and / or Subgroups
	
 ○ Korea, Republic of ○ Russian Federation ○ South Africa ○ Spain ○ Sweden ○ United States ● Baseline viral load: 
 ○ <50; ○ ≥ 50 copies/mL. ● Baseline CD4+ cell count: 
 ○ <200; ○ 200 to <350; ○ 350 to <500; ○ ≥ 500 cells/mm³. ● Derived Baseline Centres for Disease Control and Prevention (CDC) category: 
 ○ Stage I ○ Stage II ○ Stage III
EMA Subgroup Category 3:	
Additional subgroup/covariates for PK/PD efficacy analysis	
 ● Last CAB/RPV Trough PK concentration (i.e. pre-dose PK concentration wk48) ● Week-8 CAB/RPV Trough PK concentration (i.e. pre-dose PK concentration at nominal visit of Week 8) 
Dichotomized into two subgroups:
 
≤ first Quartile vs > first quartile,
 
≤ Median vs > Median,
 
The Concentration will be treated as continuous variable in logistic regression modelling analysis (i.e. the concentration data will be log₂ transformed in this analysis so that, for assessing the effect, one unit increase of the point estimate of log₂ PK concentration is equivalent to ‘doubling the concentration’ in the original value).
 
If pre-dose PK concentration at wk48 is missing, then last pre-dose PK concentration prior to WK48 will be used
 
 ● BMI (<30, ≥ 30 kg/m²) at Baseline

Category	Covariates and / or Subgroups
	
 • Length of Injection Needle (<2, ≥2 inch) For PK/PD efficacy analysis, length of injection needle at Week 4B will be used.

Additional subgroup/covariates for PK/PD safety analysis
	
 • Last CAB/RPV trough PK concentration 
For the plot of Maximum Change from Baseline(CFB) in ALT/Total Bilirubin versus Last Trough CAB/RPV PK Concentrations, Last CAB/RPV Trough PK concentration is the most recent trough PK concentration prior or equal to the date of Lab assessment with maximum CFB, at Maintenance phase
 
For the Plot of Maximum Toxicity Grades of Most Frequently Reported AEs versus Last Trough CAB/RPV PK Concentrations, Last CAB/RPV Trough PK concentration is the most recent trough PK concentration prior or equal to the onset date of the most frequently reported AE with maximum toxicity grade, at Maintenance phase. If a subject has no AE most commonly reported, then the last trough value at Maintenance phase will be used for the plot

Additional subgroup for Bone Marker analysis
	
 • BMI (kg/m2) at Baseline 
 ○ <30 ○ ≥ 30 • Smoking status: 
 ○ never, ○ current, ○ former • taking Tenofovir (TDF) at Baseline 
 ○ Yes ○ No

Additional subgroup for ISR
	
 • Length of Injection Needle (<2, ≥2 inch) for CAB and RPV, separately. 
For the summary of maximum graded ISR event by length of needle and causal agent (CAB vs RPV) will be determined based on the reported side of the ISR and the side of the previous injection administration up to and including the maximum graded ISR onset date. If we are unable to determine the needle length/causal agent in those events where both drugs are given on one side and/or their needle lengths are different, then the attribution to a needle length/causal agent will remain unknown and the ISR will be excluded from this

Category	Covariates and / or Subgroups
	summary. If there is no ISR of interest reported during maintenance phase for a subject, the needle length of last injection during Maintenance phase will be used in this summary.

5.5. Multiple Comparisons and Multiplicity

5.5.1. Primary Comparison of Interest

The primary analysis will be based on the ITT-E population. The primary comparison will be made at a one-sided 2.5% level of significance. Treatment with Q4W IM will be declared non-inferior to Current ART if the upper end of a two-sided 95% confidence interval for the difference between the two groups (Q4W IM– Current ART) in the proportion of participants with HIV-RNA ≥ 50 c/mL at Week 48 (defined by the US FDA snapshot algorithm) lies below 6%.

The primary comparison of interest is the comparison between Q4W IM and Current ART for the primary endpoint in the ITT-E population. This analysis will be adjusted for by the stratification factor applied at randomization.

If the primary analysis (Section 5.5.1) shows non-inferiority then a superiority hypothesis will be tested at the two-sided 5% level of significance. Superiority favoring CAB LA + RPV LA will be declared if the upper end of the confidence interval is below 0% for the ITT-E population analysis. If superiority is declared, the p-value for superiority will also be calculated.

5.5.2. Secondary comparison

- If the primary comparison on interest (Section 5.5.1) using the ITT-E population demonstrates non-inferiority of Q4W compared to Current ART then the following key secondary comparisons using the ITT-E population will be tested: Treatment with Q4W IM will be declared non-inferior to Current ART with respect to the proportion of participants with HIV-1 RNA < 50 copies/mL at Week 48 (defined by the US FDA snapshot algorithm) if the lower end of a two-sided 95% confidence interval for the difference between in rates (Q4W IM– Current ART) lies above -10% using the ITT-E population
- Superiority of Q4W IM compared to Current ART respect to change from baseline in HIVTSQs, at Week 44 using a two-sided 5% level of significance
- Changes in the PIN acceptance score within the CAB LA + RPV LA arm at Week 48 from Week 5 using a two-sided 5% level of significance

There are no planned adjustments for multiple comparisons or multiplicity.

For the primary endpoint treatment comparison at Week 48, no multiple comparison adjustment is necessary for testing non-inferiority followed by superiority (conditional on achieving a significant test for non-inferiority) since testing follows a pre-specified

sequence of hypothesis such that if the first hypothesis tested is not significant, all subsequent tests will not be performed. This fixed sequence procedure controls the type I error rate at the nominal level.

In addition to the primary and the key secondary comparisons, the comparisons between two treatment arms for ACCEPT (general acceptance score), SF-12 (health status), and HATQoL (Life satisfaction) at timepoints through Week 48 will also be performed as supportive analyses.

Lastly, for the IDMC interim analyses, since the statistical stopping guidelines will not result in early stopping for positive efficacy findings, these interim treatment comparisons will not inflate the Type I error rate for the primary treatment comparison.

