10.6. Planned Health Outcomes Statistical Analyses

Statistical Analyses
Endpoints
Change from Baseline in 
 ○ HIVTSQs total treatment satisfaction score at Week 4b, 24, 44 ○ ACCEPT general acceptance score at Week 8, 24, 48 ○ SF-12: Total Score, physical component summary(PCS) and mental component summary(MCS) at week 24, 48 ○ HATQoL (Life satisfaction, HIV medications, disclosure worries) at week 24, 48.
Model Specification

 • An analysis of covariance (ANCOVA) model will be used at each visit at Maintenance phase with covariates: treatment, age (<50, ≥ 50), baseline third agent class, sex at birth, and race (i.e. white, non-white) (as described in 5.4) and baseline score value (as a continuous

variable).
 
 Adjusted point estimates will be derived as LSMEAN S using the observed margins (OM) option within PROC MIXED in SAS. No adjustment for multiplicity will be applied as these analyses will be considered exploratory. Interactions between treatment and each of the covariates will not be assessed unless the exploratory subgroup analyses on the primary endpoint highlights significant interactions. In this situation, the interaction(s) of interest will be assessed and, if necessary, results will be reported in the clinical study report. Interactions between treatment and the baseline score will be investigated but not included in the model. If interactions are found to be significant, results might have to be presented separately by subgroup. No adjustment for multiplicity will be applied as these analyses will be considered exploratory.

Dataset
 
 LOCF dataset will be used.

Model Results Presentation
 
 Adjusted treatment difference (Q4W IM – Current ART), its 95% CI and the associated p-value. The interaction between treatment and the baseline score will be included in a footnote. Plots of adjusted mean change from baseline (95% CI) for each treatment group, and the adjusted mean difference (95%CI) between the two treatment arms from the model will be generated across visit.

Statistical Analyses

HIVTSQc
 
 Treatment Satisfaction Score (Change) at Week 48

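### Three key secondary tests open in parallel with the superiority test, each at full level with no order or split, and Section 10.6 calls one of them exploratory

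*SAP*

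**What the plan says.** **The gate.** SAP Section 5.5.1 sets the primary test: "The primary comparison will be made at a one-sided 2.5% level of significance".

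**Branch 1, superiority on the primary endpoint.** Section 5.5.1: "If the primary analysis (Section 5.5.1) shows non-inferiority then a superiority hypothesis will be tested at the two-sided 5% level of significance". The claim runs in one direction: "Superiority favoring CAB LA + RPV LA will be declared if the upper end of the confidence interval is below 0" (per cent). Section 7.1.5.1 repeats the rule.

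**Branch 2, the key secondaries.** Section 5.5.2 makes primary non-inferiority the only condition: "then the following key secondary comparisons using the ITT-E population will be tested". Three comparisons follow:
- non-inferiority on HIV-1 RNA <50 c/mL, judged by the lower end of a two-sided 95% interval against -10%;
- for treatment satisfaction, a between-arm test: "Superiority of Q4W IM compared to Current ART respect to change from baseline in HIVTSQs, at Week 44 using a two-sided 5% level of significance";
- for injection acceptance, a test inside one arm only, with no direction named: "Changes in the PIN acceptance score within the CAB LA + RPV LA arm at Week 48 from Week 5 using a two-sided 5% level".

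No order or alpha split is given among the three, or between them and superiority. The next sentence reads "There are no planned adjustments for multiple comparisons or multiplicity". The fixed-sequence argument that follows is limited to the primary endpoint, non-inferiority then superiority. A separate sentence places ACCEPT, SF-12 and HATQoL in a lower, supportive tier.

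**The conflicting label.** Section 10.6 covers the HIVTSQs total score at Weeks 4b, 24 and 44 and says: "No adjustment for multiplicity will be applied as these analyses will be considered exploratory". It adds that significant interactions might lead to results being presented by subgroup. Sections 5.4.1 and 7.2.5.1 use the key secondary label for the <50 c/mL endpoint only.

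**The concern.** Section 5.5.2 gives the three comparisons what a formal claim has: a gate, a stated level or interval rule for each, and a tier above the supportive analyses. Section 2.2 also lists HIVTSQs and PIN under secondary, not exploratory, objectives. A reader of the study report would take a positive result on satisfaction or injection acceptance as a formally tested finding.

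The gate gives little protection where it is most needed. If the injectable regimen really is non-inferior on the primary endpoint, the gate will usually open, and the tests behind it then add their errors together.

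The double status of HIVTSQs at Week 44 is a separate defect and does not depend on one's view of multiplicity. As written, the result could be called key or exploratory after the data are seen. Section 10.6 also leaves room to present subgroup results instead of one overall contrast.

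**Working it through.** **1. The plan's own figure.** A two-sided 95% interval read at one end gives 1 - Φ(1.96) = 0.025, the one-sided 2.5% in Section 5.5.1. Primary non-inferiority (upper limit below 6%) and superiority (upper limit below 0%) use the same interval and are nested. The sequence therefore adds no error beyond each test's own level, and the fixed-sequence statement in Section 5.5.2 is right for that pair.

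**2. Levels of the tests that the gate opens.**
- Superiority on ≥50 c/mL: 0.025 (favourable claims only, Section 5.5.1).
- Non-inferiority on <50 c/mL: 0.025 (one end of a 95% interval, Section 5.5.2).
- HIVTSQs, Week 44: 0.025 for a favourable superiority claim, or 0.05 if both directions are counted.
- PIN acceptance, Week 48 versus Week 5: 0.05 two-sided, because the text names no direction.

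**3. Independent tests, gate passed, all following nulls true.** The chance of at least one false claim is 1 - Π(1 - α).
- Four tests, superiority claims favourable only: 1 - 0.975³ × 0.95 = 11.9%.
- Four tests, HIVTSQs in both directions: 1 - 0.975² × 0.95² = 14.2%.
- Three key secondaries, HIVTSQs favourable only: 1 - 0.975² × 0.95 = 9.7%.
- Two patient-reported tests: 1 - 0.975 × 0.95 = 7.4% with HIVTSQs favourable only; 1 - 0.95² = 9.75% with both two-sided.
- Superiority plus <50 c/mL non-inferiority: 1 - 0.975² = 4.9%, against 2.5% for each.

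**4. Correlated tests.** The SAP gives no correlations. Simulated equicorrelated normal statistics give:

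| Family | ρ = 0 | ρ = 0.5 | ρ = 0.8 |
|---|---|---|---|
| Four tests, HIVTSQs favourable only | 11.9% | 10.3% | 8.2% |
| Four tests, HIVTSQs both directions | 14.2% | 12.3% | 9.6% |
| Three key secondaries, HIVTSQs favourable only | 9.7% | 8.8% | 7.4% |
| Two patient-reported, HIVTSQs favourable only | 7.4% | 7.0% | 6.4% |
| Two patient-reported, both directions | 9.75% | 9.1% | 7.8% |

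**5. Cross-check on the virologic pair.** This simulation used 285 per arm (570 randomized 1:1), an assumed ≥50 c/mL rate of 2% or 4% in both arms, and a true <50 c/mL difference of -10%. The two virologic branches together gave 4.7-4.8%, close to the independent figure.

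**The case against.** The strongest reply is that the SAP hides nothing. It says that no adjustment is planned, gives 5% as the level of each questionnaire test and not of the family, and limits its fixed-sequence claim to the pair for which it is true. That stands. A reader might infer that the SAP misstates its error control, or that the primary conclusion is weakened; the text supports neither.

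A reader might also take 14% as the plain false-claim rate. That figure counts HIVTSQs results against Q4W IM, which cannot be false superiority claims. Counted as claims, the four-test figure is 8.2-11.9% over the assumed correlations.

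The figures are also a worst case. For both virologic nulls to hold at their boundaries, the arms must have equal ≥50 c/mL rates while the <50 c/mL rate is 10 points lower on Q4W IM. Under the Snapshot categories in Section 13.11, that gap would have to be entirely extra missing virologic data. This is fair, but the point does not rest on that scenario: with both virologic tests set aside, the two patient-reported tests still give 6.4-9.75%.

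Finally, the status conflict could be called mere labelling, since Sections 5.4.1 and 7.2.5.1 reserve the key secondary term for <50 c/mL. That makes it easy to repair. It does not settle which label governs, because Section 5.5.2 explicitly includes HIVTSQs and PIN.

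**Conclusion.** The point holds in a bounded form. Gated key secondary comparisons with stated levels have no error control among themselves or alongside superiority, and HIVTSQs at Week 44 carries two incompatible statuses.

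If the primary gate is passed and every following null is true, the chance of at least one false claim is about 8-12% for the four tests, or up to 14% if HIVTSQs is counted in both directions. For the two patient-reported tests alone it is about 6-10%. These ranges rest on assumed correlations of 0 to 0.8, and fewer true nulls lower them. The 5% in Section 5.5.2 is a per-test level, so the gap is an absence of family-wise control and not a breach of a stated one. The primary non-inferiority claim is untouched.

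**What to change.** Change the SAP wording before database freeze, by one of two routes.

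**(a) Keep formal patient-reported claims.** In Section 5.5.2, state one pre-specified order or alpha split for the key secondaries, and say how it relates to the superiority test. Make this consistent with Sections 5.5.1 and 7.1.5.1, which test superiority directly after non-inferiority. Superiority should not be moved behind a within-arm PIN test: that would contradict both sections and let a questionnaire block a test that already has valid control. In Section 10.6, remove the exploratory label for HIVTSQs at Week 44 only, and name the overall ANCOVA contrast as the one tested whatever the interactions show. As an illustration of a split, 1.25% for each of four tests gives 1 - (1 - 0.0125)⁴ = 4.9%.

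**(b) Drop them.** Keep only <50 c/mL non-inferiority as the formal key secondary, at a stated step relative to superiority. Label the HIVTSQs and PIN tests supportive with nominal p-values, which agrees with how Section 10.6 already treats HIVTSQs.

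Neither route needs new data or participants. Under (a), a failed earlier step blocks later claims, or each test has a smaller alpha. Under (b), no formal patient-reported claim is made.
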